5.3.4 Sensitivity Analyses

No sensitivity analyses are planned.

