## 10.4 EFFICACY ANALYSIS

### 10.4.1 Analysis of Primary Endpoint

Clinical success rate at 6 months will be summarized using frequency (N) and percentage (%). A 95% exact CI for a single proportion will be presented for clinical success at 6 months using the Clopper-Pearson method (1934) (4). This analysis will be carried out using the PP population as the primary analysis population with the SAF population used for sensitivity analysis.

Study Protocol—Device	
Safety and Performance of MINITAC® Ti 2.0 Suture Anchor in Extremities	Number: MINI.PMCF.2018.11
	Version: 3.0, 20Aug19
	Page: Page 29 of 56

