5.2 General Presentation Considerations

As this study is of a descriptive nature, the analysis results will be reported using descriptive statistics.

Continuous data will be summarized in terms of the mean, standard deviation (SD), median, minimum, maximum and number of observations, unless otherwise stated. Continuous data that are expected to be skewed will be presented in terms of the maximum, upper quartile, median, lower quartile, minimum and number of observations. The minimum and maximum will be reported to the same number of decimal places as the raw data recorded in the database. The mean, median, lower quartile and upper quartile will be reported to one more decimal place than the raw data recorded in the database. The SD will be reported to two more decimal places than the raw data recorded in the database. In general, the maximum number of decimal places reported shall be four for any summary statistic.

Categorical data will be summarized in terms of the number of subjects providing data at the relevant time point (n), frequency counts and percentages. Percentages will be presented to one decimal place. Percentages will not be presented for zero counts. Percentages will be calculated using n as the denominator.

Given the small, convenience study sample, as well as the absence of *a priori* statistical hypotheses, no formal tests of statistical significance are planned, and as such, no p-values or statistical intervals will be calculated.

All report outputs will be produced using SAS[®] version 9.3 or a later version in a secure and validated environment. All report outputs will be provided to the Sponsor as individual .rtf files and as a consolidated .pdf document.

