5.6 Handling of Missing and Uninterpretable Data

Missing data will not be imputed, and the data will be analyzed as they were entered in the study database.

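### The 6- and 12-month success rates cover only subjects with data, and no planned output shows the rate over the full analysis set under any assumption about unassessed subjects

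*SAP*

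**What the plan says.** SAP 5.3.2 and 5.3.3 report clinical success at 6 and 12 months as a frequency and percentage. Success is a composite of six items that must all hold. SAP 5.3.2 says the analyses use the FAS, but gives no rule for an enrolled subject who has no assessment in the window.

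The general rules fill that gap:
- SAP 5.2: "Categorical data will be summarized in terms of the number of subjects providing data at the relevant time point (n), frequency counts and percentages", followed by "Percentages will be calculated using n as the denominator".
- SAP 5.6: "Missing data will not be imputed".
- SAP 5.3.4: "No sensitivity analyses are planned".

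SAP 5.2 and 5.8 also drop p-values and confidence intervals, so the percentage stands without any statement of uncertainty.

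Protocol 10.4.1 had planned the per-protocol set as primary, "with the SAF population used for sensitivity analysis". SAP 5.8 replaces both sets with the single FAS.

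**The concern.** An observed-case percentage equals the rate in all enrolled subjects only if unassessed subjects succeed as often as assessed ones. Nothing in this design guarantees that. Eligibility requires more than 12 months since surgery but not a follow-up visit in the chart (Protocol 7.2). Data are taken as far as the chart allows (Protocol 9.1.3 and 9.1.4). Loss to follow-up means not returning under the surgeon's own schedule (Protocol 7.7), and no prospective visit can fill a gap (Protocol 7.5).

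The direction of any bias is unknown. A patient with a failed repair might be treated elsewhere, and a patient who is well might not come back. What matters is scale: at the assumed 95% success rate, the expected number of failures is 0.05 × 30 = 1.5 to 0.05 × 50 = 2.5. A few unassessed subjects can outnumber them.

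**Working it through.** **The plan's own figures.** Protocol 11 and SAP 5.7 give probabilities of 55.4% (N = 30) and 98.8% (N = 50) of meeting ±10% precision at 95% true success. Taking the criterion as a Clopper-Pearson 95% interval with half-width of at most 0.10:
- N = 30 needs at least 29 successes. P(X ≥ 29) = 0.3389 + 0.2146 = 0.5535.
- N = 50 needs at least 44 successes. P(X ≥ 44) = 0.9882.

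Both match with all 30 or 50 subjects evaluable. Protocol 8.3.3 says attrition was allowed for, but these figures show no allowance, so no expected missing rate can be recovered from them.

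**Inputs.** N is 30 or 50 (SAP 5.7). The observed success rate is taken close to the planned 95%. The share unassessed is not in the documents; 10% and 20% are assumptions.

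**Formulas.** With m subjects unassessed and s successes among the N − m assessed:
- reported rate = s / (N − m)
- lower bound (unassessed = failure) = s / N
- upper bound (unassessed = success) = (s + m) / N
- gap between the bounds = m / N

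**Results.**

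| N | m | Reported | Lower bound | Upper bound | Gap |
|---|---|---|---|---|---|
| 30 | 3 | 26/27 = 96.3% | 26/30 = 86.7% | 29/30 = 96.7% | 10 points |
| 30 | 6 | 23/24 = 95.8% | 23/30 = 76.7% | 29/30 = 96.7% | 20 points |
| 50 | 5 | 43/45 = 95.6% | 43/50 = 86.0% | 48/50 = 96.0% | 10 points |
| 50 | 10 | 38/40 = 95.0% | 38/50 = 76.0% | 48/50 = 96.0% | 20 points |

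The reported rate barely moves as m grows, while the lower bound falls by about 10 points for each 10% unassessed.

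**Do other planned outputs fill the gap?**
- The 3-9 month estimate (SAP 5.3.2) changes which assessment dates count. A subject with no assessment is still left out.
- The person-month rates (SAP 5.3.2, 5.3.3) and the Kaplan-Meier analysis (SAP 5.3.3) use partial follow-up. They cover only device failure and/or device-related re-intervention, not the six-item composite.
- The disposition table (SAP 5.4.1) and the by-subject listing (SAP 5.3.3) hold the raw material, but present no rate over all FAS subjects.

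**The case against.** Much of the case on the other side is sound.

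*The effect is not hidden.* The disposition table counts subjects enrolled and completing each visit, the listing gives success status by subject, and n is shown with each percentage. A careful reader could work out the bounds. This stands: the gap is that the report does not show them, not that they are unobtainable.

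*Missingness may be small.* The 6-month window runs from day 182 − 150 = 32 to day 182 + 30 = 212, so one chart entry from about a month after surgery onward qualifies. This stands, and it makes 10-20% less certain at 6 months. The SAP 3.5.3 warning of much missing data concerns surgeon reported outcomes, so it is no evidence about clinical success.

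*The lower bound is extreme.* The 76.7% figure requires all six unassessed subjects to have failed, against a planned failure rate of 5%. True; it is a bound, not an estimate.

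*The FAS is the stated set for all analyses, so the denominator might be all enrolled.* That reading is possible, but SAP 5.2 holds the only explicit denominator rule and it points to subjects with data. On either reading the SAP must say how an unassessed subject counts.

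*The study is descriptive, with no hypothesis or pass mark.* True, and this limits the severity. Bounds are themselves descriptive and need no test or model.

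A reader might also infer that the SAP cancelled a missing-data check promised in the protocol. The documents do not support that. Under Protocol 10.2 the per-protocol and safety sets differ by significant deviations and eligibility, not by availability of the outcome. The SAP's FAS is defined almost exactly as the protocol's safety set. Restoring the protocol's comparison would not show the effect of unassessed subjects.

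**Conclusion.** The point holds as a reporting gap. SAP 5.2, 5.6 and 5.3.4 together make both success rates observed-case rates, and no planned output gives the composite over the full FAS under any assumption about unassessed subjects. The size depends on a missing rate that the documents do not state. At an assumed 10% to 20% of 30 subjects, a reported rate of about 96% would have a lower bound of 86.7% to 76.7%. The gap of 10 points per 10% unassessed is arithmetic and does not depend on the success rate.

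Two stronger readings should be avoided. One is that the worst case breaches an 85% limit: at 10% unassessed it does not (86.7% and 86.0%), and 85% is the lower end of an anticipated confidence interval, not a success threshold. The other is that the reported rate is known to be biased: that absence depends on outcome is plausible in either direction, but the documents do not establish it. The change is worth making because it costs almost nothing and the rate rests on one or two expected failures.

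**What to change.** Replace the text of SAP 5.3.4 so that, at 6 and at 12 months, the report shows:
- the number of FAS subjects assessed and not assessed;
- the observed-case success rate;
- the rate over all FAS subjects with unassessed subjects counted as failures;
- the rate over all FAS subjects with unassessed subjects counted as successes.

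Count any failure or re-intervention documented before the window as a failure, even where there is no later visit. State in 5.3.2 that the observed-case rate uses subjects with data and that the two bounds use the full FAS. Define unassessed there too, including how a subject with some of the six items blank is classified, so that the rows can be reproduced.

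The cost is one extra row or table per endpoint, from data already collected, and a less favourable lower figure on display. If few subjects are unassessed, the bounds will be narrow and will support the reported rate.

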5.3.5 Analysis of the Other Endpoints

5.3.5.1 ROM

The number and proportion of patients with full functional arc will be presented. In addition, summary statistics (N, mean, SD, median, and range) will be calculated at 6 months and 12 months within side, body location and motion direction (i.e., internal, external).

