**Table 9.1-1: Study Procedures by Visit**

Schedule of Events	Chart Review 		
	Screening	6 months (182 days) post-op (+30/- 150 days)	12 months (365 days) post-op (+30/- 150 days)
Inclusion/Exclusion	X		
Demographics/Medical History	X		
Operative Data Collection	X		
Assessment of clinical success (device related re-intervention and/or repair failure)		X	X
Surgeon Reported Outcomes: Pain assessed by VAS 	X	X	X
Surgeon Reported Outcomes: ROM 	X	X	X
Concomitant Medications or Therapies	X	X	X

Study Protocol—Device	
Safety and Performance of MINITAC® Ti 2.0 Suture Anchor in Extremities	Number: MINI.PMCF.2018.11
	Version: 3.0, 20Aug19
	Page: Page 25 of 56

All Adverse Events or Complications, Device Deficiency (DD)	X	X	X
AE Assessment	X	X	X
End of Study			X

 Given the retrospective study design, data will be collected to the extent it is available.

 Surgeon Reported Outcomes are collected per standard of care.

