**----- Do not proceed until consent or waiver of consent has been obtained -----**
3. Assign the subject a Subject ID.
4. Collect the following retrospective data, to the extent it is available, from the subject's medical chart and complete the associated CRFs:
  - Obtain demographic information and medical history.
  - Obtain operative data including discharge.
  - Obtain surgeon reported outcomes as defined in section 8.2.3 to the extent available for the pre-operative time point.
  - Collect Adverse Events and Device Deficiencies from enrollment until discharge and intraoperative complications.
  - Collect concomitant medications or therapies.

Study Protocol—Device	
Safety and Performance of MINITAC® Ti 2.0 Suture Anchor in Extremities	Number: MINI.PMCF.2018.11
	Version: 3.0, 20Aug19
	Page: Page 26 of 56

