#### 10.4.3 Analysis of Other Endpoints

Available data based on data collected from the subject's medical chart as standard of care at study sites will be summarized and summary statistics tabulated.

- The derivation of surgeon reported outcomes will be described in the SAP and will be summarized as appropriate using descriptive summary characteristics for continuous or categorical endpoints. Differences from screening/baseline to 6 months and 12 months will be similarly summarized and/or compared. The details of distributional assumptions of the test statistics used will be described in the SAP.

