3.5.3.1 Surgeon Reported Outcomes

Surgeon reported outcomes include specific data collected as standard of care and documented in the medical records. This will include:

- Range of Motion (ROM)
- Pain assessed by Visual Analogue Scale (VAS)
- Device Failure Criteria

A listing of device failure criteria will be collected for subjects that were assessed by the surgeon to have signs of device failure and/or re-intervention and therefore not meeting the definition of clinical success.

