5.3.5.2 VAS

Summary statistics (N, mean, SD, median, and range) will be calculated for the raw data and for their absolute and percent change from baseline by scheduled visits.

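### SAP 5.3.5.1 gives continuous range-of-motion results only at 6 and 12 months, without the baseline differences planned in Protocol 10.4.3, so they cannot show whether motion improved or worsened after repair

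*SAP*

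**What the plan says.** Protocol 8.2.3 names ROM and VAS pain as surgeon reported outcomes. The procedures table (Table 9.1-1) marks ROM at screening, 6 months and 12 months. Protocol 9.1.2 tells sites to "Obtain surgeon reported outcomes as defined in section 8.2.3 to the extent available for the pre-operative time point".

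Protocol 10.4.3 covers these outcomes as a class: "The derivation of surgeon reported outcomes will be described in the SAP and will be summarized as appropriate using descriptive summary characteristics". It continues: "Differences from screening/baseline to 6 months and 12 months will be similarly summarized and/or compared".

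SAP 3.5.3.1 lists ROM, VAS and device failure criteria as outcomes that will be included. The analyses then differ:

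- **ROM (SAP 5.3.5.1):** "The number and proportion of patients with full functional arc will be presented", with no time point given. For the continuous data, "summary statistics (N, mean, SD, median, and range) will be calculated at 6 months and 12 months within side, body location and motion direction".
- **VAS (SAP 5.3.5.2):** the raw values and their "absolute and percent change from baseline by scheduled visits".
- **Other surgeon reported outcomes (end of SAP 5.3.5.3):** descriptive summaries, with differences from baseline to 6 and 12 months.

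SAP 5.3.1 defines baseline as the last non-missing pre-operative value. SAP 5.8 lists four changes from the protocol, and none concerns ROM or change from baseline.

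**The concern.** The study is meant to assess safety and performance after repair. For ROM, that means asking whether the joint moves more, less or the same as before surgery. A post-operative mean cannot separate stiffness that was there before the operation from motion lost after it.

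Missing data add to the difficulty. SAP 3.5.3 expects many surgeon reported values to be missing and SAP 5.6 rules out imputation, so different patients may contribute at different visits. A reader who tries to rebuild the change by setting separate visit means side by side may be comparing different people.

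There is also a documentation issue. Protocol section 10 says the SAP will report changes from the analyses projected in the protocol. If ROM change was left out on purpose, SAP 5.8 is where that should appear.

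**Working it through.** The documents give no figure for this point, so the check is mainly a comparison of texts.

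**Step 1. Does the protocol's baseline comparison cover ROM?** Yes. Protocol 10.4.3 speaks of surgeon reported outcomes as a class, and Protocol 8.2.3 lists ROM in that class.

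**Step 2. Is a baseline value foreseen?** Yes. ROM is scheduled at screening, sites are told to extract the pre-operative value where the chart has one, and SAP 5.3.1 defines baseline.

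**Step 3. What does the SAP specify for each named outcome?**

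| Outcome | Pre-operative value scheduled | Baseline summary | Change from baseline |
|---|---|---|---|
| VAS pain | Yes | Yes (raw data by visit) | Yes, absolute and percent |
| ROM, continuous | Yes | Not specified | Not specified |
| ROM, full functional arc | Yes | No time point stated | Not specified |
| Device failure criteria | Not applicable | Not applicable | Not applicable |
| Other outcomes, if entered | As available | As appropriate | Yes |

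ROM is the only named outcome with a scheduled pre-operative value and no change summary.

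**Step 4. Does another sentence restore it?** The last sentence of SAP 5.3.5.3 repeats the baseline-difference plan. It follows text about other outcomes that may be entered in the database and sits outside the ROM subsection. On its wording it does not reach ROM.

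**Step 5. Is the omission declared?** No. The four changes in SAP 5.8 concern tests and intervals, analysis sets, Kaplan-Meier event rates, and the 3-to-9-month window.

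**Step 6. What can the planned results show?** Take illustrative means of 110 degrees at 6 months and 118 degrees at 12 months. These and the baselines below are assumptions, not document values. Change is the follow-up mean minus the baseline mean:

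| Assumed baseline | Change at 6 months | Change at 12 months |
|---|---|---|
| 90 | 110 − 90 = +20 | 118 − 90 = +28 |
| 110 | 110 − 110 = 0 | 118 − 110 = +8 |
| 130 | 110 − 130 = −20 | 118 − 130 = −12 |

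The same planned output fits a gain, no early change, or a loss. The post-operative summaries do not fix even the sign.

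**The case against.** **The protocol leaves room.** Protocol 10.4.3 hands the derivation to the SAP and asks for summaries as appropriate. Protocol 8.2.3 calls these outcomes optional and lists ROM as something that might be collected. This stands as a limit on how binding the plan is. However, SAP 3.5.3.1 then commits to ROM, and the SAP applies the baseline comparison to VAS, which has the same status.

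**The sentence in SAP 5.3.5.3 may have been meant for all surgeon reported outcomes.** It nearly repeats the protocol's sentence, so misplacement is plausible. A reader might infer that the sponsor deliberately dropped ROM change. The documents do not show that, and loose drafting explains the gap equally well. Either way, an analyst following 5.3.5.1 would not produce the change.

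**ROM is not limited to post-operative means.** The proportion with full functional arc can be read without a baseline, and a baseline proportion is not excluded. It would therefore be wrong to call paired change the only interpretable summary. But no time point is specified, and two proportions are not a within-subject change.

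**Paired change need not be more precise.** A reader might infer a precision gain from SD(change)/SD = √(2(1−r)), where r is the correlation between baseline and follow-up and variances are equal. With assumed r of 0.8 this is √0.40 = 0.63; with 0.5 it is 1.00; with 0.3 it is 1.18; with 0 it is 1.41. The documents give no r. Paired N can only equal or fall below visit N, and the standard errors are equal when paired N / visit N = 2(1−r). At r = 0.8 the gain is gone once fewer than 40% of visit subjects have a baseline; at r = 0.5 it is never there. The SAP also plans no intervals. This objection stands in full.

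**Pairing does not remove all case-mix differences.** Subjects with pairs at 6 months need not be those with pairs at 12 months, so the two change columns may still describe different people. Restricting to pairs is itself a selection. This stands too.

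**Conclusion.** The point holds as a minor one. The SAP leaves continuous ROM without the baseline summary and change from baseline that Protocol 10.4.3 plans, and SAP 5.8 does not say so. The consequence is limited to interpretation: those results cannot tell improvement from deterioration relative to the pre-operative state. The primary and secondary endpoints are unaffected, and ROM is exploratory and available only where the charts record it.

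The conclusion rests on reading the closing sentence of SAP 5.3.5.3 as confined to other outcomes, which its wording and position support. It does not rest on any assumed correlation, standard deviation or amount of missing data.

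**What to change.** In SAP 5.3.5.1:

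1. Add a baseline summary of ROM.
2. Add the absolute change from baseline at 6 and 12 months among subjects with both values, and report the paired N at each visit. Use the side, location and direction cells already planned.
3. Present full functional arc at baseline, 6 and 12 months.

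If ROM change is to be left out on purpose, state and justify that in SAP 5.8 instead.

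The cost is a few extra columns in a planned table. No new data collection or baseline definition is needed. The real drawback is sparse cells, because pre-operative ROM is extracted only where the chart has it. As a rough guide, assume two sides, the five locations in SAP 3.3 and one side and location per subject. Then 30 to 50 subjects spread over 2 × 5 = 10 cells average 3 to 5 per cell before any missing values. The post-operative summaries already planned face the same limit, and the paired N lets the reader judge each cell.

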5.3.5.2 VAS

Summary statistics (N, mean, SD, median, and range) will be calculated for the raw data and for their absolute and percent change from baseline by scheduled visits.

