### **7.2 INCLUSION CRITERIA**

Subjects will be considered qualified for enrollment if they meet the following criteria:

1. Subject has undergone extremities repair using the MINITAC◇ Ti 2.0 Suture Anchor.
2. Subject was  $\geq$  18 years of age at time of surgery.
3. Subject status is  $>$  12 months post-operative.

Study Protocol—Device	
Safety and Performance of MINITAC◇ Ti 2.0 Suture Anchor in Extremities	Number: MINI.PMCF.2018.11
	Version: 3.0, 20Aug19
	Page: Page 17 of 56

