3.5.3 Other Endpoints

Additional endpoints include surgeon reported outcomes as well as safety endpoints. There is expected to be a large volume of missing data associated with the surgeon reported outcomes.

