5.3 Statistical methods

5.3.1 General Analysis Definitions

Screening / Enrollment: For screening, only information available in the medical records will be reviewed. When all inclusion criteria and none of the exclusion criteria have been met for a subject and the informed consent process has been completed or a waiver of consent has been granted by the HREC/EC, the subject will be considered enrolled.

Baseline: Unless specified otherwise, the last non-missing value before study product installation/operation collected at the screening visit is considered as the baseline value.

Study Day:

Study Day = assessment date – study product installation/operation date + 1 for assessments post operation;

Study Day = assessment date – study product installation/operation date for assessments prior to operation;

All durations are calculated as the stop date minus the start date +1 unless otherwise specified.

End of Study: Due to the retrospective design of the study, end of the study is defined as the date when the last subject is documented on CRFs.

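### The planned mean percent change in VAS pain has no rule for a baseline of 0 and can be dominated by one low baseline

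*SAP*

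**What the plan says.** SAP 5.3.5.2 asks for N, mean, SD, median and range "for the raw data and for their absolute and percent change from baseline by scheduled visits". The mean and SD of individual percent changes are therefore planned output.

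The denominator is fixed by SAP 5.3.1, where "the last non-missing value before study product installation/operation collected at the screening visit is considered as the baseline value". It sets no minimum and does not mention zero. SAP 5.6, although its heading covers uninterpretable data, says only: "Missing data will not be imputed, and the data will be analyzed as they were entered in the study database". SAP 5.3.4 adds: "No sensitivity analyses are planned".

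Eligibility (Protocol 7.2 and 7.3) asks for a repair with the anchor ("Subject has undergone extremities repair using the MINITAC" Ti 2.0 device), adult age at surgery, more than 12 months since surgery, and no other investigational study or product. It sets no pain threshold.

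On sample size, the protocol plans 30 to 50 subjects and makes surgeon reported outcomes optional (8.2.3). SAP 3.5.3 warns: "There is expected to be a large volume of missing data associated with the surgeon reported outcomes".

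Protocol 10.4.3 promises only differences from baseline to 6 and 12 months for these outcomes. SAP 5.3.5.1 plans no percent change for range of motion. Percent change for VAS is an SAP addition that the list of changes in SAP 5.8 does not mention.

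**The concern.** There are two separate weaknesses, both from dividing by the baseline.

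First, a subject with baseline 0 has no percent change. With no rule and no imputation, that subject drops out of the line. A subject at 0 can stay at 0 or get worse but cannot improve, so the loss is not neutral: worsening from zero cannot appear in the percent-change summary.

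Second, a subject with a low but non-zero baseline can contribute a change of several hundred percent. Reductions are bounded at -100% and increases are not, so one such subject can govern the mean, especially when few subjects have VAS at both time points.

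At stake is one descriptive line that could be misread, or could point the opposite way from the absolute change printed next to it. A related, smaller matter is that raw means at each visit are taken over whoever has data. With much missingness, the baseline, 6-month and 12-month raw means may describe different subjects. The absolute-change line does not share this fault, because each change needs both values.

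**Working it through.** The plan states no figure on this point, so there is nothing to reproduce. The check uses constructed scores. Neither document gives the VAS range or a baseline distribution; **a 0-10 scale and all scores below are assumptions**.

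Formulas, for baseline *b* and follow-up *f*:
- absolute change = *f* - *b*
- percent change = 100 × (*f* - *b*)/*b*, undefined at *b* = 0
- ratio of means = 100 × (mean change)/(mean baseline)

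**1. A small worked table.** Baselines 8, 6, 5, 1, 0; follow-up 2, 1, 1, 3, 2.
- Absolute changes: -6, -5, -4, +2, +2. Mean = -11/5 = -2.2 (N = 5).
- Percent changes: -75, -83.3, -80, +200, undefined. Mean = -38.3/4 = -9.6% (N = 4). Median = (-80 - 75)/2 = -77.5%. Range -83.3% to +200%.
- Ratio of means: baseline mean 20/5 = 4.0, so 100 × (-2.2/4.0) = -55% (N = 5).

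**2. Zero baselines.** Thirty subjects: 30 - k go from 6 to 2, and k go from 0 to 2.

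| k | Mean % change (N) | Mean absolute change, all 30 | Ratio of means, all 30 |
|---|---|---|---|
| 1 | -66.7% (29) | (29 × -4 + 2)/30 = -3.8 | -65.5% |
| 3 | -66.7% (27) | (27 × -4 + 6)/30 = -3.4 | -63.0% |
| 6 | -66.7% (24) | (24 × -4 + 12)/30 = -2.8 | -58.3% |

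The percent-change mean does not move as more subjects worsen from zero. The absolute change does.

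**3. One low baseline.** All other subjects go from 6 to 2 (-66.7% each); one subject is added.

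| Added subject | Own % change | Mean %, 29 + 1 | Mean %, 9 + 1 | Mean absolute, 29 + 1 | Mean absolute, 9 + 1 |
|---|---|---|---|---|---|
| 1 to 4 | +300% | -54.4% | -30.0% | -3.77 | -3.30 |
| 0.5 to 4 | +700% | -41.1% | +10.0% | -3.75 | -3.25 |
| 0.1 to 2 | +1900% | -1.1% | +130.0% | -3.80 | -3.41 |
| 0.2 to 5 | +2400% | +15.6% | +180.0% | -3.71 | -3.12 |

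For example, (9 × -66.7 + 700)/10 = (-600 + 700)/10 = +10.0%. The median stays at -66.7% in every row. In four of the eight means the sign is opposite to that of the absolute change.

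**The case against.** The strongest reply is that the planned table already gives the reader much of what is needed. N is reported for each line, so a drop from 5 to 4 would show. Median and range are reported too; in the first example a median of -77.5% beside a mean of -9.6% points to a single outlier. SAP 5.2 also has a general rule: "Continuous data that are expected to be skewed will be presented in terms of the maximum, upper quartile, median, lower quartile, minimum", which leaves out the mean. This stands in part. The median and range expose a dominating value but not the outcomes of the dropped subjects. A smaller N does not say why they are missing, least of all where much missingness is expected. The skewness rule does not name VAS, and SAP 5.3.5.2 lists mean and SD for it.

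Three stronger readings are tempting, and the documents do not support them.
- *Subjects who worsen are excluded from the VAS analysis.* They are not. Zero-baseline subjects leave one line of three, and some of them may simply stay at 0.
- *The percent-change line favours the device.* Dropping a subject who worsens from zero flatters the line, but a low-baseline subject who worsens penalises it. In the first example -9.6% looks worse for the device than -55%.
- *Zero baselines will be common.* The indications in Protocol 6.1 include instability and ligament repairs, where pain need not be the main complaint, but also hallux valgus and lateral epicondylitis. The documents give no basis for a frequency.

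It is also fair to say that stating a zero-baseline rule and the excluded N would close the first gap without deleting anything. It would leave the unstable mean in place.

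**Conclusion.** The point holds as a minor defect in a descriptive summary. Followed as written, SAP 5.3.5.2 yields a mean percent change that omits any subject with baseline 0 and can be governed by one low baseline. That percent change is undefined at zero, and that no rule covers it, follows from the SAP text and needs no assumption. The sizes do: on an assumed 0-10 scale, one low-baseline subject moved a mean of -66.7% to between -54.4% and +15.6% with 30 subjects, and to between -30.0% and +180.0% with 10. The net direction is unknown, and so is the number of subjects affected.

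The consequence is small. VAS is an optional exploratory outcome, summarised without tests or intervals. The primary and secondary endpoints do not use it.

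**What to change.** In SAP 5.3.5.2:
- Delete percent change and rely on absolute change from baseline. This is what Protocol 10.4.3 asks for.
- Beside each absolute change, show N and the baseline and follow-up means of the same paired subjects, separately for 6 and 12 months.
- If a relative figure is wanted, give 100 × (mean change/mean baseline) in the paired subjects. Alternatively, give only the median percent change and state how many zero-baseline subjects were excluded.

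The cost is an edit to one SAP line, with little effect on programming. One descriptive line is lost. The ratio of means gives more weight to subjects with high baselines, which a footnote should say if it is used.
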